We propose to conduct a multicenter, randomized, placebo-controlled, double-blind clinical trial that will evaluate the efficacy of adjuvant dexamethasone (0.15 mg/kg per dose, twice daily for 3 days) in preventing renal scarring in young febrile children (2 months to 6 years) with a first-diagnosed UTI. 520 participants will be enrolled over a 3.75-year period from 6 sites. Choice of antimicrobial treatment and need for follow-up imaging will be at the discretion of the providing physician. If possible, the study nurse will demonstrate how to give the child the study medication and will administer the first dose to the child, otherwise study medication will be administered to the child no later than 48 hours after the first dose of antibiotic treatment for the UTI. A flavoring syrup will be mixed by the parent before each separate dose

Figure 3. Study Design

with the medication/ placebo to make the study medication flavor more appealing to the child. The parent will draw the prescribed amount of medication/ placebo from the syringed-top medication bottle and push it out into a small medication cup provided by the study team. The parent will then draw an equivalent amount of flavoring syrup from the flavoring bottle using a separate dosing syringe and push the flavoring out into the same medication cup. The parent will then mix the contents in the medication cup. After mixing, the child will be able to drink the contents directly from the medication cup or the parent will re-draw the contents using the syringe and administer the contents to the child with the dosing syringe. The study medication will be given with meals, twice daily to reduce gastrointestinal side effects. If vomiting occurs within 20 minutes of steroid administration, an equivalent second dose will be administered. We will ask that the study medication doses administered to the child be recorded in a medication diary that will be provided by the study. When the child has completed the study, we will ask that the parent return all medication supplies and the medication diary in a postage-paid box that will be provided by the study.

II. Recruitment

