The proportion of children who have any renal scars on the outcome DMSA scan in each treatment arm will serve as the principal outcome variable. Renal scarring will be defined as decreased uptake of tracer with or without loss of contours. We will also compare the proportion of children with severe scarring between groups. Severe scarring will be defined as the presence of grades 3 or 4 scarring on at least one kidney. Three reference radiologists, blinded to treatment assignment, will make all determinations and the reading endorsed by the majority will be used as the primary outcome measure. The analysis will follow intent to treat principles: subjects will be analyzed according to randomized treatment assignment regardless of adherence. Children who are found to have a negative urine culture will not be included in the efficacy analysis. These children do not have a UTI and are not at risk for developing renal scarring. Up to 6% of children (n=23) are expected to have a recurrent UTI in the follow-up period.²² It is estimated that for most of these children (~85%), the recurrent UTI episode will not result in renal scarring. As such, the effect of re-infections on the primary analysis will be minimal. The incidence and the extent of renal scarring in the two treatment groups will be compared using logistic regression. We will also test for statistical interaction for individual variables (age, gender, race, mother's education, fever duration, infecting organism, CRP, ibuprofen use within 24 hours of enrollment, and 5 preselected urinary biomarkers listed below) and steroid treatment. This is done to investigate the possibility that the relative treatment effect differs among patient subgroups. We are aware that tests for interaction generally have low statistical power and we will likely detect only marked differences in treatment effects in these subgroups. Furthermore, the additional problem of falsely identifying heterogeneity of treatment effect among patient subgroups in clinical trials is well known and therefore the interpretation of subgroup differences is considered exploratory and will be done with caution. Another analysis will be the proportion of children with recurrent febrile UTIs in each treatment group.

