Data will be analyzed after approximately one third of enrolled children complete the outcome DMSA scan. If there is a significant difference between groups, the DSMB may consider the possibility of terminating the study. Type I error will be controlled by using the method of Fleming, Harrington and O'Brien. Testing will be conducted at significance levels of 0.005 and 0.048 at the interim and final analysis, respectively.⁷⁸

We will also compare the mean proportion of scarring in the two treatment groups across the three radiologists while adjusting for the correlation resulting because the radiologists evaluated the same set of scans.

Because some of the STARRs participants also participated in the companion “Biomarkers for Pyelonephritis” study, in which early DMSA scan is performed to determine whether pyelonephritis is present, we will examine the efficacy of treatment in children with and without pyelonephritis.

The study will be powered to detect a 10% difference between the two arms. A 10% absolute difference between the two groups translates into a number needed to treat of 10 (i.e., 10 children will need to be treated to prevent one child from developing scars). Assuming a 15% rate of scarring in the control group, a two-sided alpha of 0.05, a beta of 0.8, a 10% attrition rate, and a 7% rate of false positive urinalysis, 190 children will be required per group (i.e., 160 evaluable children per group). However, as the study progressed, we realized that 30% of children enrolled had a false positive urinalysis, and thus increased the required sample size to 260 children per group (to arrive at the 160 evaluable children needed). The 15% rate of scarring in the control group comes from a meta-analysis we conducted.⁷⁹ The attrition rate is based on our previous study of intravenous versus oral antibiotics for the treatment of UTI which was also a randomized multicenter study with a 6-month follow-up DMSA.²²

A recent study described several urinary biomarkers that appear promising in differentiating children with pyelonephritis from children with cystitis.⁸⁰ Because only children with pyelonephritis are at risk for renal scarring, these markers could potentially be used to select children for treatment with adjuvant corticosteroids. As such we will examine for interactions between 5 such biomarkers and treatment effect. Logistic regression

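### Do the interim and final levels of 0.005 and 0.048 lose control of type I error because the interim is set at one third of enrolled children?

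*Combined protocol and SAP*

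**What the plan says.** Section C.VI (Statistical Analysis) times the single interim look as follows: "Data will be analyzed after approximately one third of enrolled children complete the outcome DMSA scan". It then says: "Type I error will be controlled by using the method of Fleming, Harrington and O'Brien", and fixes the levels: "Testing will be conducted at significance levels of 0.005 and 0.048 at the interim and final analysis, respectively". A significant interim difference does not stop the trial by itself; the DSMB may consider termination. The overall level is a two-sided 0.05.

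The same section excludes some enrolled children: "Children who are found to have a negative urine culture will not be included in the efficacy analysis". Because 30% of enrolled children turned out to have a false positive urinalysis, the sponsor "increased the required sample size to 260 children per group (to arrive at the 160 evaluable children needed"). Section C.I (Design) carries the resulting total: "520 participants will be enrolled over a 3.75-year period from 6 sites". The full information for the primary comparison is thus 320 evaluable scans, 160 per arm. The plan does not restate the interim as a number out of 320.

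**The concern.** A fixed pair of levels holds a given overall error only for certain information fractions. The pair 0.005 and 0.048 is, to rounding, the two-look O'Brien-Fleming boundary at half of the information. The plan speaks of one third, and of enrolled rather than evaluable children. Enrolled (520) and evaluable (320) differ widely, and the plan does not say outright whether culture-negative children are scanned or count toward the third. An early look would make the interim and final statistics less correlated, so the same two levels would add up to more than 0.05. The stated control of type I error would then depend on a count that appears nowhere in the plan.

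**Working it through.** **Inputs.** From section C.VI: levels 0.005 and 0.048, two-sided 0.05, control rate 15%, difference 10 points, attrition 10%, false positive urinalysis 7% and later 30%. The stated beta of 0.8 is read as power 0.80. From the aim and section C.I: 320 evaluable, 520 enrolled.

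**1. The plan's own sample size.** For 15% against 5%, with pooled rate 0.10:

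n = [1.960·√(2·0.10·0.90) + 0.842·√(0.15·0.85 + 0.05·0.95)]² / 0.10² = 140.1, so 141 per arm.

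With the continuity correction, n′ = (140.1/4)·[1 + √(1 + 4/(140.1·0.10))]² = 159.5, so 160. This is the plan's figure. The inflation also agrees to within 3%: 160/(0.90·0.93) = 191 against the stated 190, and 160/(0.90·0.70) = 254 against the stated 260. Full information is therefore 320 scans.

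**2. Where the levels come from.** The classical two-look O'Brien-Fleming boundary computes to 0.0052 and 0.0480 at half of the information, and to 0.0007 and 0.0497 at one third. The plan's pair fits a look at half.

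**3. Overall error under normal theory.** With t = (evaluable scans at the interim)/320 and correlation √t between the two statistics:

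α(t) = 1 − P(|Z₁| < 2.807 and |Z₂| < 1.977)

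| Reading of one third | Evaluable scans | t | Overall error |
|---|---|---|---|
| 320/3, counting evaluable children | 107 | 0.33 | 0.0509 |
| 520/3 × 0.70 × 0.90, first third enrolled, after losses | 109 | 0.34 | 0.0509 |
| 380/3 × 0.93, former target, culture-negative counted | 118 | 0.37 | 0.0507 |
| 520/3 × 0.70, culture-negative scanned and counted | 121 | 0.38 | 0.0507 |
| 380/3, former target, all evaluable | 127 | 0.40 | 0.0506 |
| 520/3, all evaluable | 173 | 0.54 | 0.0497 |

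The error equals 0.05 at t = 0.488, or 156 of 320 scans.

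**4. Which reading the text supports.** Taken literally, the count is of enrolled children who have completed the scan, and current enrolment is 520, which gives 173.

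- The reading of 107 puts evaluable in place of enrolled.
- The reading of 109 deducts attrition from children who, by the plan's wording, have already completed the scan.
- The readings of 118 and 127 use the 380 that the plan has replaced.
- The readings of 118 and 121 need culture-negative children to be scanned and counted. Section C.V.D times the scan from the index UTI, or from the last UTI after a re-infection. Section C.VI says that culture-negative children have no UTI and are not at risk of scarring. Scanning only culture-positive children is the natural inference, though the plan does not state it.

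**5. Is 49% a real dividing line?** The outcome is binary and the analysis is logistic regression. I enumerated the exact error for an unadjusted comparison with 53, 60, 64, 80 or 87 children per arm at the interim, 160 at the end, and a common scarring rate of 10% or 15%. Tables with a zero cell counted as non-significant for Wald.

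| Test | Error, all timings | Error at 80 per arm (160/320) |
|---|---|---|
| Wald | 0.0448–0.0462 | 0.0449, 0.0462 |
| Score | 0.0498–0.0515 | 0.0501, 0.0508 |
| Likelihood ratio | 0.0511–0.0560 | 0.0532, 0.0515 |

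Wald holds 0.05 at every timing, one third included. Likelihood ratio exceeds it at every timing, half included. The score test is marginally above it even at half. The normal-theory crossover at 156 scans therefore does not decide whether 0.05 is held.

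**6. What an adjustment would achieve.** With 0.005 kept at the interim, the final level that restores 0.05 under normal theory is 0.0470 at 107 scans, 0.0473 at 121 and 0.0474 at 127, against the planned 0.048. Power of the final test for 15% against 5% goes from 0.846 at 0.048 to 0.844 at 0.047.

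**The case for a change.** The best case for a change is that a plan claiming control of type I error should state the count on which the claim depends. The levels fit a look at half of the information and the text says one third. Five of the six readings above fall short of 156 scans, and a correction costs no patients and about 0.002 of power.

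Part of this stands. The interim is not given as a number of evaluable scans, the levels do match a half-information look, and the normal-theory figures are right. The rest carries little weight. A tally of readings says nothing about how likely each one is, and the one closest to the current text holds 0.05. The shortfall on the others is below 0.001, and the proposed repair does not secure control for the test actually used: moving the look to 160 scans leaves the score and likelihood-ratio tests above 0.05.

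**Conclusion.** The concern does not call for a change. The plan leaves a gap that its analysts can fill sensibly: when the look is taken, the number of evaluable scans is known and can be reported with it. The most that depends on it is an overall error of 0.0509 instead of 0.05. Even that requires every interim crossing to count as a rejection, whereas the plan leaves stopping to the DSMB's judgement. If only the final test counted, the normal-theory error would be 0.048.

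This rests on three assumptions: 320 evaluable children at the end, information proportional to evaluable scans, and an interim no earlier than about one third of that information. A look at 80 of 320 scans would still give only 0.0514. The exact figures are for an unadjusted comparison. Followed as written, the plan gives a sound primary test, and a rewritten timing rule would bring no real gain.
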